8.7.3. Safety Analysis

Summaries and listings of AEs and other safety parameters will be provided by period of treatment (Sunitinib, Axitinib).

Frequencies of patients experiencing at least one AE will be displayed by body system and preferred term according to MedDRA terminology. Summary tables will present the number of patients observed with AEs and corresponding percentages.

The description will be conducted for all the reported AEs whether related to the drug or not, and then for the AEs related to SU or AXI.

Adverse event reported by patients through the quality of life questionnaires will also be described.

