10. MANAGEMENT AND REPORTING OF ADVERSE EVENTS/ADVERSE REACTIONS

10.1. REQUIREMENTS

The table below summarizes the requirements for recording safety events on the eCRF of the study and for reporting safety events on the non-interventional study (NIS) adverse event monitoring (AEM) Report Form to Pfizer Safety. These requirements are delineated for three types of events: (1) serious adverse events (SAEs); (2) non-serious AEs (as applicable); and (3) scenarios involving drug exposure, including exposure during pregnancy, exposure during breast feeding, medication error, overdose, misuse, extravasation, and occupational exposure. These events are defined in the section "Definitions of safety events".

Safety event	Recorded on the eCRF of the Study	Reported on the NIS AEM Report Form to Pfizer Safety within 24 hours of awareness
SAE	A11	A11
non-serious AE	All	All Potential risks (SUNITINIB RMP V14.0) Carcinogenicity Other Potential Cardiac events: Conduction defect events, Ischemic events, Tachycardia events Retinal detachment Reproductive and developmental toxicity Missing Information (SUNITINIB RMP V14.0) Use in pediatric subjects Use in pregnant and lactating women Use in severe hepatic impairment subjects Use in cardiac impairment subjects Use in cardiac impairment subjects Potential risks (AXITINIB RMP V8.0) Wound healing complications Congestive heart failure/cardiomyopathy QT prolongation Reproductive and developmental toxicity Microangiopathy Carcinogenicity Osteonecrosis of the jaw Drug Drug interactions with CYP1A2, CYP2C8 and P-glycoprotein substrates Missing information (AXITINIB RMP V8.0) Risks in pregnant and lactating women,
		Risks in pediatric subjects,

		Risks in patients with moderate and severe renal impairment (serum creatinine >1.5 times the ULN or calculated creatinine clearance <60 mL/min), Risks in subjects with severe hepatic impairment (>Child-Pugh Class B), Risks in patients with brain metastasis, spinal cord compression, or carcinomatous meningitis, Risks in subjects with recent myocardial infarction, severe/unstable angina, coronary/peripheral artery bypass graft, symptomatic congestive heart failure, cerebrovascular accident or transient ischemic attack, deep vein thrombosis, or pulmonary embolism, Risks in patients with active peptic ulcer disease, Appendix 1.1.1. Risks in subjects with a recent major surgery (within 4 weeks) or radiation therapy (within 2 weeks).

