Scenarios involving exposure to a drug under study, including exposure during pregnancy, exposure during breast feeding, medication error, overdose, misuse, extravasation; lack of efficacy; and occupational exposure	All (regardless of whether associated with an AE), except occupational exposure	All (regardless of whether associated with an AE)

For each AE, the investigator must pursue and obtain information adequate both to determine the outcome of the adverse event and to assess whether it meets the criteria for classification as a SAE (see section "Serious Adverse Events" below)

Safety events listed in the table above must be reported to Pfizer within 24 hours of awareness of the event by the investigator regardless of whether the event is determined by the investigator to be related to a drug under study. In particular, if the SAE is fatal or life-threatening, notification to Pfizer must be made immediately, irrespective of the extent of available event information. This timeframe also applies to additional new (follow-up) information on previously forwarded safety event reports. In the rare situation that the investigator does not become immediately aware of the occurrence of a safety event, the investigator must report the event within 24 hours after learning of it and document the time of his/her first awareness of the events.

For safety events that are considered serious or that are identified in the far right column of the table above that are reportable to Pfizer within 24 hours of awareness, the investigator is obligated to pursue and to provide any additional information to Pfizer in accordance with this 24-hour timeframe. In addition, an investigator may be requested by Pfizer to obtain specific

follow-up information in an expedited fashion. This information is more detailed than that recorded on the eCRF of the study. In general, this will include a description of the adverse event in sufficient detail to allow for a complete medical assessment of the case and independent determination of possible causality. Any information relevant to the event, such as concomitant medications and illnesses must be provided. In the case of a patient death, a summary of available autopsy findings must be submitted as soon as possible to Pfizer or its designated representative.

Reporting period

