ADONIS CRF Subject ID: Other treatments Additional anti-tumor treatment (e.g. bisphosphonates, other) (the previous visit anti-tumor treatment table is dispalyed) Has additional anti-tumor treatment been changed since last visit (including during this visit)? ☐ Yes □ No If yes please update the table: Medication Dosage Starting date Status __/ ___ ■ Ongoing ■ Discontinued (MM/YYYY) (trade name) End date : ___ / _____ (unit) (dose) (MM/YYYY) □ Ongoing □ Discontinued (MM/YYYY) End date : _ _ / _ _ _ _ (trade name) (dose) (unit) (MM/YYYY) (new lines can be added if more than 2 medications are received) ☐ No Radiotherapy :

Yes Comedications (other than tumor therapy): (the previous visit comedication table is displayed) Have comedications been changed since last visit (including during this visit)? ☐ Yes □ No If yes please update the table: Drug name Starting date Status □ Ongoing □ Discontinued (MM/YYYY) End date ___ / __ ___ (MM/YYYY)) □ Ongoing □ Discontinued (MM/YYYY) End date ___ / __ __ (MM/YYYY)) (new lines can be added if more than 3 treatment s are received)

ADONIS CRF Subject ID: Occurrence of adverse events Has the patient experienced adverse events since last visit? ☐ Yes ☐ No If yes please report the adverse events in the following table and asses the grade using the CTCAE V4.03 (this version is reachable via ta click) Adverse event description Starting date Grade (CTCAE V4.03) □ 2 □ 3 □ 4 (DD/MM/YYYY) □ 1 □ 2 □ 3 □ 4 (DD/MM/YYYY) (new lines can be added if more than AR have occured) Please completed an AE form per AE reported in the table (AE form is attached in annex 2) (The eCRF, automatically completes any section when data are already available; the pre-completed sections are still editable /An AE form per AE is completed The safety requirement as described in the protocol are reminded via a click)

ADONIS CRF Subject ID:

Actions done at the end of this visit with Sunitinib					
☐ Continuation: Please completed this said	me form at the next visit				
☐ Temporary Interruption Please update the					
(the table is disp	layed to the investigator)				
☐ Discontinuation	□ Discontinuation				
If discontinuation, reasons of disco	ontinuation (no multiple selections)				
	Date/ (DD/MM/YYYY)				
☐ Intolerability	Date/ (DD/MM/YYYY)				
main reason:					
☐ Death	Date of death// (DD/MM/YYYY)				
Cause:	☐ tumor-related				
	☐ other cause				
Please observe the definitions and AE rep	orting requirements as defined in the protocol				

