Was Sunitinib dosa	ge or sch	nedule change	ed durir	ng Sunitini	b course? 🗆 Y	'es □ No	
Il yes please specify changes :							
Date	Change of dosage	(mg/day		sage	Change of schedule	If yes, new schedule	
	☐ Yes	□ 25	□ 37.	5	□ Yes		_
	□ No	□ 50	□ 62 .	5	□ No		_
(DD/MM/YYYY)		□ 75	□ Oth	ner: 🎞			
	□ Yes	□ 25	□ 37.	5	□ Yes		_
	□ No	□ 50	□ 62 .	5	□ No		_
(DD/MM/YYYY)		□ 75	□ Oth	ner: 🎞			
Was Sunitinib temporarily interrupted during the course? ☐ Yes ☐ No Il yes please specify interruptions : First day of interruption ☐ Duration in days interruption ☐ If yes, reason							
				☐ Adverse events ☐ Radiotherapy			
(DD/MM/YYYY)				□ Surger	y	□ Other	
				Adverse	events □ Ra	diotherapy	
(DD/MM/YYYY)				☐ Surger	У	□ Other	
(new lines can be added if more than 2 interruptions occurred)							
Reason for disc	ontinuat	tion of SUNI	ITINIE	3 □ Ye	s 🗆 No		
☐ Progression,	Date	/	/	الله (100	D/MM/YYYY)		
☐ Intolerance	Date	/	ــــــــــــــــــــــــــــــــــــــ	ال الــــــــــــــــــــــــــــــــــ	D/MMYYYY)		
	Pleas	se specify the	e sym _l	ptom whic	ch you consid	lered decisive	
Other	(mair	n reason)					
	definitio	ons and AE a	nd sei	rious AE 1	eporting requ	uirements in the protocol.	

ADONIS CRF					Subject I
Has the patient experienced advers ☐ Yes ☐ No	e events related to Sunitinib dur i	ing the t	reatment	course?)
If yes please report the adverse eve (this version is reachable via le lien)		ses the g	rade usi	ng the C	TCAE V4.0
Adverse event description	Starting date		Grade	(CTCAE	V4.03)
	///	□ 1	□ 2	□ 3	□ 4
	LLLL/LL (DD/MM/YYYY)	□ 1	□ 2	□ 3	□ 4
(new lines can be added if more tha	n AR have occurred)				
Please completed an AE form per A	E reported in the table (AE form	is attac	hed in ar	nnex 2)	
(The eCRF, automatically completes sections are still editable /An AE for		dy availa	ible ; the	pre-com	pleted
The safety requirement as described	in the protocol are reminded via	a click)		

4.2. AXITINIB Follow-up	VISIT
-------------------------	-------

Axitinib fo	ollow-up visit	Date —— / .	/ 20 (D	D/MM/YYYY) Pa	itient identifier ᆜᆜ		
Please check	that the patient ha	s completed the	e OoL questionnaire	before coming at the	visit		
If not, please ask him to complete the questionnaire, preferentially prior to the visit							
Tumor asse	essment accordi	ing to RECIS	ST criteria (V1.1))			
Was	tumor assessment o	dono sinco lost u	visit? □ Yes	□ No.			
Date	or the assessment		(JUMINUT)	,			
lmagi	ing procedure (mult	iple selections p	ossible)				

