Current Axi	tinib do	sage						
(the CRF displa	ys the do	sage scheduled at t	he previou	s visit)				
Has the Axitinib	dosage or	schedule been chang	ged since th	ne last docume	ented visit (including during this vi	isit)?		
☐ Yes ☐ No								
II yes please sp	ecify char	iges:						
Date	Dose red	uction		Dose titration	on up			
	☐ Yes	new dosage		□ Yes	new dosage			
	□ No	☐ 7 mg/2x/day		□ No	□ 10 mg/2x/day			
(DD/MMADA)		☐ 5 mg/2x/day			□ 7 mg/2x/day			
(DD/MM/YY YY)		☐ 3mg/2x/day			☐ 5 mg/2x/day			
		☐ 2mg/2x/day			☐ 3mg/2x/day			
		□ Other: ᆜᆜmg	/2x/day		☐ Other: ☐☐mg/2x/day			
	Reason f	or dose reduction		Reason for d	ose titration up			
	☐ Intolera	ance		☐ Good tolerance ☐ Inefficacity				
	☐ Other,			□ Other,				
(new lines can	be added	f more changes ha	ve occurre	ed)				
		ily interrupted since I	ast visit?	l Yes L	□ No			
II yes please sp	ecity inter	ruptions :						
First day of interruption		Duration in days	If yes, ne	w schedule				
			☐ Advers	se events	☐ Radiotherapy			
(DD/MM/YYYY	′)		□ Surger	у	□ Other			
(new lines can	(new lines can be added if more than 2 interruptions occurred)							

Other treatments						
Additional anti-tumor	treatment (e.g. bisphos	sphonates, others	s)			
(the previous visit anti-tumor treatment table is displayed)						
Has additional anti-tumor treatment been changed since last visit (including during this visit) ? ☐ Yes ☐ No						
If yes please update the ta	ble:					
Medication	Dosage	Starting date	Status			
	11		☐ Ongoing ☐ Discontinued			
(trade name)	(dose) (unit)	(MM/YYYY)	End date : —] / —] —] — (MM/YYYY)			
	/		☐ Ongoing ☐ Discontinued			
(trade name)	(dose) (unit)	(MM/YYYY)	End date :			
			(MM/YYYY)			
(new lines can be added if	more than 2 medications	are received)				
Radiotherapy : Yes		□ No				
Comedications (other	than tumor therapy) :	(the previous visit	t comedication table is displayed)			
Have comedications been c	hanged since last visit (includ	ling during this visit)	? □ Yes □ No			
If yes please update the ta	ble:					
Drug name	Starting date	Status				
		□ Ongoing □ Di	scontinued			
	(MM/YYYY)		(MM/YYYY))			
	(MM/YYYY)	□ Ongoing □ Di				
	\	End date/	LLL (MM/YYYY))			
(new lines can be added if more, than 2 treatment's are received)						

Safety							
Has the patient experienced adverse events related to Sunitinib during the treatment course? ☐ Yes ☐ No							

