If yes please report the adverse events in the following table and asses the grade using the CTCAE V4.03 (this version is reachable via ta click)							
Adverse event description	Starting date	Grade (CTCAE V4.03)					
	UL/UL/UL/UL/UL/UL/UL/UL/UL/UL/UL/UL/UL/U	□1 □2 □3 □4					
	UL/UL/ULUU (DD/MM/YYYY)	1 2 3 4					
(new lines can be added if more than AR have occured)							
Please completed an AE form per AE reported in the table (AE form is attached in annex 2)							
(The eCRF, automatically completes any section when data are already available; the pre-completed sections are still editable /An AE form per AE is completed / The safety requirement as described in the protocol are reminded via a click.)							

Actions done at the end of this visit with AXITINIB								
☐ Continuation: Please completed this same form at the next visit								
☐ Temporary Interruption Please update the temporary interruption table								
(the table is displayed to the investigator) □ Discontinuation								
If discontinuation, reasons of discontinuation (no multiple selections)								
☐ Progression Date ☐ / ☐ / ☐ / ☐ (DD/MM/YYYY)								
☐ Intolerability Date ☐ / ☐ / ☐ / ☐ (DD/MWYYYY) main reason								
☐ Death Date of death ☐ (DD/MM/YYYY) Cause ☐ tumor-related ☐ other cause								
Please observe the definitions and AE and reporting as defined in the protocol								
If discontinuation, will the patient start a 3 nd line therapy? : □ Yes □ No								
If yes, which drug will the patient receive?								
Name of the drug								
Date of start								
Dose								
Scheduled Please completed the long term follow-up visit every 6 months								
ricase completed the long term follow-up visit every o months								
Please complete the "Follow-up visit" at each visit until discontinuation of Sunitinib								
Follow up visit are not scheduled by the study but are based on routine care visits. They are expected to approximately every 4 weeks								

ADONIS CRF Subject ID:

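### The adverse event question on the annexed axitinib follow-up CRF asks only about sunitinib-related events, which conflicts with protocol section 10.1 and risks under-recording in the axitinib period

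*Protocol*

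**What the plan says.** In Annex 1, CRF section 4.2 (axitinib follow-up visit), the Safety block has one screening question: "Has the patient experienced adverse events related to Sunitinib during the treatment course". A yes leads to a table of events with description, start date and CTCAE grade. The site is then asked for one Annex 2 adverse event form per event entered in that table. A note on the form adds: "The safety requirement as described in the protocol are reminded via a click". The form ends by telling sites to complete the follow-up visit "at each visit until discontinuation of Sunitinib".

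The matching question on the sunitinib follow-up form (CRF section 3.2) has no relatedness filter: "Has the patient experienced adverse events since last visit".

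Protocol section 10.1 sets the recording rule. It introduces its table with "The table below summarizes the requirements for recording safety events on the eCRF of the study", and the eCRF column requires all SAEs and all non-serious AEs. Events listed for 24-hour reporting go to the sponsor "regardless of whether the event is determined by the investigator to be related to a drug under study". Table 1 lists sunitinib and axitinib AE description and grade as an outcome taken at follow-up visits. The CRF study plan marks safety for collection at the axitinib follow-up visit.

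On analysis, protocol section 8.7.3 says "The description will be conducted for all the reported AEs whether related to the drug or not", and then turns to related events. SAP section 6.2.1 separates sunitinib-related from axitinib-related events. SAP section 8.2.1 tabulates events overall and by treatment period, sunitinib and axitinib.

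**The concern.** The form meant to collect axitinib-period events screens on a relationship to the previous drug. A site that answers it literally can truthfully say no for a patient with axitinib-related diarrhoea or an unrelated infection. The event table and the Annex 2 form then do not open from that page.

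Describing safety and tolerability of the SU-AXI sequence is a stated secondary objective, and an AE listing in patients receiving axitinib is a listed endpoint. The analysis covers reported events, so an event that is not recorded simply does not appear. Patients enrolled at sunitinib start would be asked an open question in one period and a restricted, wrong-drug question in the next, yet the SAP presents the two periods together. A lower axitinib rate could then partly reflect the question asked, and sites could differ in how they read it.

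**Working it through.** The plan states no figure that depends on this question, so the check compares the forms with the rules and analyses they serve.

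**1. The AE questions across the CRF**

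| Form | Scope of the question |
|---|---|
| Sunitinib follow-up (3.2) | Any event since last visit |
| Axitinib initiation, retrospective sunitinib section (4.1) | Events related to sunitinib during the treatment course |
| Axitinib follow-up (4.2) | Events related to sunitinib during the treatment course |

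The restriction fits the middle row, where past sunitinib treatment is abstracted from records. In the last row it does not match the drug being taken. The closing instruction on the same form also names sunitinib, whereas the axitinib initiation page tells sites to complete the axitinib follow-up page until axitinib stops. Two wrong drug names on one form point to a copying error rather than a choice.

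**2. Against the recording rule and the analyses**

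Section 10.1 requires all events on the eCRF. Table 1 and the CRF study plan expect axitinib safety data at follow-up. The SAP needs axitinib-period and axitinib-related counts. A question limited to sunitinib-related events cannot supply any of these by itself.

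**3. What the other routes recover**

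- *Annex 2 form.* It asks about relatedness to the study drug, not to sunitinib alone. On this visit form, however, it is requested per event already entered in the table, so it sits behind the restricted question.
- *24-hour reporting.* Outside Switzerland, the non-serious events reportable within 24 hours appear to be limited to listed risk-management-plan items (the table is partly broken in the text). None of the ten event types that SAP section 6.2.1 describes whatever their frequency, among them diarrhoea, hypertension, fatigue and hand-foot syndrome, is on that list by name. Entries defined by patient group may catch some of them. Otherwise, when non-serious, they depend mainly on the eCRF.
- *Reasons for interruption, dose reduction and discontinuation.* These catch only events that changed treatment.
- *Questionnaire prompt.* It tells patients to inform their doctor, which enters nothing in the eCRF. Section 8.2 also exempts some patients from the questionnaires.
- *Monitoring.* Section 8.8.2 checks CRF data against source. A truthful no to the sunitinib question can pass that check.

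**4. Exposure to the wording**

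Inputs: 350 SU-AXI patients (section 8.5); visits about every 4 weeks, or 28 days (section 8.2); 6.5 months as a stand-in for time on axitinib (investigator-assessed AXIS PFS, section 6); 30.44 days per month (SAP).

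- Visits per patient: 6.5 × 30.44 / 28 = 7.07, about 7
- Form completions: 350 × 7 = 2,450

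This approximates how often the question would be put. It does not count missed events. It uses a median PFS from another trial as average treatment time, and the visits are not mandated. The documents give no axitinib event rate and no share captured by each route, so the number of lost events cannot be derived.

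**The case against.** The strongest reply is that section 10.1 is itself an eCRF recording rule, not only a rule for reporting to the sponsor. A site that follows it records every axitinib event whatever the screening question says. The form carries a reminder of the safety requirements, and intolerance or adverse events can be given as reasons for interruption, reduction or discontinuation. SAP section 6.2.2 draws discontinuations due to AEs from both the follow-up forms and the AE forms. The long-term follow-up form has its own AE question. The annexed CRF is V12.2 of 5 December 2014, attached to protocol V13 of 28 September 2017, so the wording in the live eCRF is unknown.

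Most of this stands, and it rules out several stronger readings.

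- A reader might infer that axitinib events are not collected at all, or that the axitinib tables will be incomplete and biased downward. The documents do not show this, because section 10.1 and the other routes remain in force.
- A reader might infer that late sunitinib events would be counted as axitinib events. Each event has a start date, Annex 2 names the causal drug, and the SAP separates events by related drug.
- A reader might infer from the closing instruction that axitinib follow-up stops early. The axitinib initiation page gives the right drug, and the form asks to be completed again at the next visit if treatment continues.

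What does not stand is the suggestion that these routes remove the problem. A general duty in section 10.1 and a form question that contradicts it leave each site to choose between them, and the partial routes miss non-serious events that led to no action.

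**Conclusion.** The question is wrong as written and should be corrected. It conflicts with section 10.1, Table 1 and the planned safety tables, and no passage gives a reason for the restriction. The consequence is a risk, not a demonstrated loss: possible under-recording of axitinib-period events, chiefly non-serious ones with no treatment change, and unequal ascertainment between the two periods. For patients enrolled at sunitinib start, that inequality is an open question against a restricted one.

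The loss lies between none (all sites follow section 10.1) and substantial (sites answer literally), and the documents do not narrow that range. About 2,450 form completions would carry the wording, on the assumptions given with that calculation. The conclusion assumes that the annexed form reflects what sites saw, which cannot be confirmed here. The primary endpoints, PFS and TTF, do not depend on this question.

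**What to change.** 1. Check the wording in the live eCRF first.
2. In CRF section 4.2, replace the question with the one already used on the sunitinib form, "Has the patient experienced adverse events since last visit", and record relatedness on the adverse event form.
3. Align the completion instruction at the end of that form with the axitinib initiation page, so that it names axitinib.
4. If the restricted wording was live, query negative answers against source. Reconcile the eCRF events with the safety database and with the recorded reasons for interruption, dose reduction and discontinuation. The safety database alone may not recover common non-serious events.
5. State any remaining limitation beside the axitinib safety tables and wherever the two periods are shown together.

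The cost is one wording change and, if the error was live, a query round. No new patients, visits or procedures are needed.
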